#### C. Study Design and Research Methods

This study is an open label, cross-over study, evaluating the plasma and peritoneal fluid pharmacokinetics of dalbavancin after either intravenous or intraperitoneal administration. The

patients will be randomly assigned to receive dalbavancin either intravenously or intraperitoneally on study visit 1. The patients will receive the alternate administration technique following the washout period at visit 4. Patients will be administered dalbavancin either intravenously or intraperitoneally on study day 0. Pharmacokinetic analysis will be conducted on days 0, 7, and 14. Following the wash out period of 45 days or greater, the same 10 patients will cross-over and then be administered dalbavancin via the alternate administration technique received in visit 1 on study day 0. Pharmacokinetic analysis will be conducted again on days 0, 7, and 14. (see Appendix 1)

*Sample Size:*

Ten (n=10) patients will be evaluated in this pharmacokinetic evaluation. Since this is a descriptive pharmacokinetic study a sample size calculation was not performed

*Plasma and peritoneal fluid sampling:*

Dalbavancin will be administered on study day 0. On the intravenous administration day dalbavancin will be administered as a 30-minute IV infusion. On the intraperitoneal administration day, dalbavancin will be administered in the peritoneal dialysis fluid with a 6 hour dwell time. On day 0, patients will undergo plasma and peritoneal fluid pharmacokinetic sampling for determination of dalbavancin concentrations at time zero, 1 hour, 2 hours, 3 hours, 4 hours, 6 hours, at time of volume exchange. Patients will be given a specimen collection cup and asked to collect ~30 ml of peritoneal dialysate following scheduled nocturnal dwell approximately 24 hours following the administration of dalbavancin administration. Patients will report for a single PK measurement on study days 7 and 14. (18 total plasma and 18 total peritoneal fluid samples per patient). Blood samples will be drawn from a peripherally inserted intravenous catheter. Peritoneal fluid samples will be drawn from the already placed peritoneal dialysis catheter. Blood samples will be immediately centrifuged at 3000g and plasma and peritoneal fluid samples will be stored at -80°C until analysis.

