**D. Description, Risks and Justification of Procedures and Data Collection Tools:**

**Enrollment and Screening:** Study subjects will be contacted an enrolled through [name] clinic. Initial contact will be made by phone prior to a clinic appointment to discuss initial interest of the patient. Further information and enrollment will take place at a clinic visit or time of the patients choosing. Enrollment will take place in a private room at [name] clinic. Initial baseline and demographic information will be gathered for enrolled patients at the time of enrollment. Safety labs (comprehensive metabolic panel and urine pregnancy test for women of childbearing potential) will be drawn or performed at [name] clinic and will coincide with a scheduled clinic visit closest to study protocol initiation. The comprehensive metabolic panel will be drawn to evaluate Child-Pugh score if there is no comprehensive metabolic panel within the medical record within 30 days of protocol initiation.

**Visit 1 and 4:** (~8 hours): On visits 1 and 4 the patients will undergo intensive PK sampling. Inclusion and exclusion criteria will be reviewed with the patient at each visit prior to initiation of the protocol. Subjects will be admitted to the CTRC in the morning and a "saline-lock" will be placed. The dalbavancin preparations will be prepared and managed by [name] or [name] who are both clinical pharmacists with training in sterile drug preparation. The dalbavancin 1500 mg will either be administered, by CTRC nursing staff, intravenously (as randomly assigned) or into the intraperitoneal space (as randomly assigned) using the patient's existing peritoneal dialysis catheter with the patients currently prescribed dialysate. Following the blood and peritoneal fluid collection at the second dialysis volume exchange, the subjects will be discharged and asked to return at a scheduled time on day 7. Patients will also be given a specimen collection up with instructions to collect approximately 30 ml of peritoneal dialysate following their evening nocturnal dwell. The collected dialysate will be returned to the investigators.

**Visit 2, 3, 5, and 6:** (~60 minutes): A "saline-lock" will be placed and a single blood and peritoneal fluid sample will be collected at each of these visits. All blood and peritoneal fluid draws will be

completed at the outpatient CTTC. The patient will be discharged and follow up visits will be scheduled for day 14 or next intensive PK sampling visit.

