##### *Pharmacokinetic analysis:*

Plasma and peritoneal fluid concentration-time data for dalbavancin will be evaluated using a multi-compartment model in Phoenix WinNonlin (Pharsight corporation). One, two, and three compartment models will be explored. The following PK parameters will be calculated for plasma and dialysate samples: Cmax – measured, Tmax – measured, Cmin – measured. Fraction of intraperitoneal (IP) dose absorbed [(Dose – drug concentration remaining in dialysate at end of

antibiotic dwell)/Dose].  $K_{el}$  – elimination rate constant.  $T_{1/2} = 0.693/K_{el}$ .  $K_{pc0-6}$  – rate constant for distribution of dalbavancin from peritoneal cavity between 0-6 hours. Distribution half-life in the peritoneal cavity between 0-6 hours ( $t_{1/2} = \ln 2/k_{pc0-6}$ ). Clearance systemic =  $(F \times \text{Dose})/AUC_{0-\infty}$ . Clearance peritoneal – dalbavancin concentration in spent dialysate/AUC of peritoneal fluid. Non-dialysis clearance –  $Cl = Cl_{plasma} - Cl_{peritoneal}$ .  $AUC_{0-\infty}$  – linear trapezoidal method.  $AUC_{0-12}$  hours – linear trapezoidal method. Volume of distribution for each compartment –  $Cl/k_{el}$ ; nonsteady state equations will be utilized. The ratio of plasma dalbavancin to dialysate plasma concentration at each time point –  $C_{plasma}/C_{dialysate}$  and via  $AUC_{plasma}/AUC_{dialysate}$ . Given the sample size of 10 patients completing each treatment modality we will be able to calculate means and standard deviations for all included pharmacokinetic parameters. We will incorporate the dalbavancin PK parameters into a nonlinear mixed effects model (NONMEM) or ADAPT II to determine the pharmacokinetics and examine the effects of varying dosing strategies on plasma and peritoneal fluid concentrations.

*Analysis of pharmacodynamic targets:*

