Pharmacodynamic parameters will be evaluated in order to determine whether dalbavancin dosing results in initial and steady-state plasma and peritoneal concentrations that are adequate for treatment of infections due to common pathogens (Staph aureus, Coag neg staph, and enterococcus). Monte Carlo simulation (Crystal Ball version 7, Decisioneering, Inc., Denver, CO) will be used in this study to calculate probability of target attainment (PTA) for pharmacodynamic goals. The model randomly applies values for  $C_{max}$  and  $AUC_{0-12}$  derived from data obtained from the study patients. We will utilize CLSI and EUCAST MIC data for the common gram positive pathogens. We will place these MIC distributions into our Monte Carlo simulation for comparison to dalbavancin plasma concentrations and PK variability. From these studies, MIC frequency distributions will be constructed and used in the Monte Carlo simulations. Ten thousand simulations will be performed at each MIC value and for each of the selected pathogens.

[figure not shown]
[figure not shown]
*Statistical comparisons of PK/PD findings*

Intra-patient pharmacokinetics and pharmacodynamics of dalbavancin will be compared between intravenous and intraperitoneal administration using the paired-t test. Given the sample size of 10 patients completing each phase of the study, we will be able to detect a mean difference in area under the curve between the two treatment modalities of 1527 mg·hr/L at a power of 80%. Probability of target attainment will be compared with the paired t-test. Statistical comparisons will be compared using SAS version 9.3. A p-value < 0.05 will be considered significant.

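### F in the systemic clearance formula is undefined, and the only fraction the plan offers, loss of the intraperitoneal dose from dialysate, is not systemic bioavailability and can misstate clearance by route.

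*Combined protocol and SAP*

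**What the plan says.** Under Pharmacokinetic analysis in Section IV.F, "Clearance systemic" is given as (F × Dose)/AUC0-∞. F is not defined for either route, and F = 1 for IV is not stated.

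The same list contains one fraction, the "Fraction of intraperitoneal (IP) dose absorbed". It is the dose minus the "drug concentration remaining in dialysate at end of" the antibiotic dwell, divided by the dose. This subtracts a concentration from an amount, and no volume appears.

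The planned ratios set plasma against dialysate: "The ratio of plasma dalbavancin to dialysate plasma concentration at each time point", and the corresponding AUC ratio. The ratio of plasma AUC after IP dosing to plasma AUC after IV dosing is not listed.

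Non-dialysis clearance is plasma clearance minus peritoneal clearance, and volume is clearance over the elimination rate constant, so both inherit whatever F is used.

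Under Statistical comparisons of PK/PD findings: "Intra-patient pharmacokinetics and pharmacodynamics of dalbavancin will be compared between intravenous and intraperitoneal administration using the paired-t test". Clearance is not named there, but it is one of the listed pharmacokinetic parameters.

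**The concern.** Drug that has left the dialysate has not necessarily reached the circulation, and drug left in the cavity at the drain may be absorbed later. Dialysate loss and systemic bioavailability are therefore different quantities. Clearance belongs to the patient and not to the route, so if dialysate loss stands in for F, an apparent route difference in clearance can arise from the formula alone.

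Plasma pharmacokinetics by both routes is part of the primary endpoint (Section IV.A). A misstated IP clearance would carry into non-dialysis clearance and volume, and possibly into the NONMEM or ADAPT II model meant to explore other dosing strategies. The design makes this avoidable, because each patient receives 1500 mg by both routes.

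**Working it through.** **The plan's own figure.** The only design figure is a detectable AUC difference of 1527 mg·hr/L with 10 patients at 80% power. No SD is given, so it cannot be reproduced. A two-sided paired t-test at 0.05 implies an SD of the paired difference of 1527/0.996 = 1533 mg·hr/L. The figure concerns AUC, and nothing below depends on it.

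**Inputs from the documents.** Dose 1500 mg by either route (Section IV.D, Visit 1 and 4); 6-hour IP dwell (Section IV.C); half-life about 8.5 days (Section II); last sample on day 14. The dialysate is each patient's own prescription ("with the patients currently prescribed dialysate"), so its volume is not given.

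**Assumed inputs.** Volume 1.5 to 3 L; share of the dose still in the cavity at 6 h, R = 0.3 to 0.7; share of the cavity contents left after draining, r = 0.05 to 0.15.

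**Step 1: the identity.** Let f_a be dialysate loss and F = AUC_IP/AUC_IV, with true clearance the same in both periods. Then CL_IP/CL_IV = (f_a × Dose/AUC_IP)/(Dose/AUC_IV) = f_a/F. With F itself in the formula, CL_IP = Dose/AUC_IV = CL_IV in every patient, and the paired difference is zero by construction.

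**Step 2: the formula as printed, concentration in mg/L.** At 2 L and 50% true loss, 750 mg remains, or 375 mg/L. Then f_a = (1500 − 375)/1500 = 0.75, and 0.75/0.50 = 1.50. At 1.5 L and 3 L the ratio is 1.33 and 1.67. At 2 L with true loss of 30%, 70% and 90% it is 2.17, 1.21 and 1.06.

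**Step 3: amounts, counting only drained drug as unabsorbed.** f_a = 1 − R(1 − r). If all residual drug is rinsed out, F = 1 − R. If later dwells absorb like the first, F = (1 − R)/(1 − rR). Overstatement is f_a/F − 1:

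| R | Residual rinsed out, r = 0.05 to 0.15 | Later dwells absorb like the first, r = 0.05 to 0.15 |
|---|---|---|
| 0.3 | 2.1% to 6.4% | 0.6% to 1.6% |
| 0.5 | 5.0% to 15.0% | 2.4% to 6.4% |
| 0.7 | 11.7% to 35.0% | 7.8% to 20.8% |

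For example, R = 0.5 and r = 0.15 give f_a = 0.575. Against F = 0.50 the ratio is 1.150; against F = 0.5/0.925 = 0.5405 it is 1.064.

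**Step 4: amounts, counting all drug in the cavity as unabsorbed.** f_a = 1 − R. The ratio is 1 if the residual is rinsed out, and 1 − rR if later dwells absorb like the first: 0.985 at R = 0.3, r = 0.05, and 0.895 at R = 0.7, r = 0.15.

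**Step 5: check with a plasma–cavity mass-balance model.** Assumed: non-dialysis clearance 0.04 L/h, plasma volume 12 L, cavity 2 L, transfer 0.2 L/h. With no residual fluid the ratio is 0.96 to 1.00, depending on how much drug passes back from plasma. With 10% residual it is 1.06 counting drained drug only and 0.94 counting all cavity drug. The sign depends on the convention.

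**Step 6: effect on a test.** For a paired t-test on log clearance with n = 10, a purely artefactual 1.25-fold ratio would be called significant with probability 0.99, 0.71, 0.44 or 0.24 at an assumed SD of the log difference of 0.15, 0.25, 0.35 or 0.50. For a 1.1-fold ratio the values are 0.43, 0.19, 0.12 and 0.08.

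**The case against.** The symbol F is never attached to the dialysate-loss fraction. The investigators may have meant bioavailability, and the compartmental or population model could estimate it. That is fair: the link is an inference. It does not remove the problem, because no other candidate for F appears in the text, and if another was meant, F is simply undefined for the IP route and needs the same wording change.

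A reader might infer that IP clearance is necessarily biased upward. The documents do not support this. They do not say which volume would turn the concentration into an amount, and Steps 4 and 5 show ratios at or below 1. The upper end of 35% also needs all residual drug to be lost, although the same membrane could go on absorbing it.

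A reader might also infer that a clearance test is explicitly planned and would measure only the error in F. Clearance falls within the general term for pharmacokinetics but is not named. Such a test would also carry period variation, assay noise and extrapolation error in AUC0-∞: with a mono-exponential 8.5-day half-life, 0.5^(14/8.5) = 32% of the AUC lies beyond day 14.

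Finally, the consequences are limited. The power statement concerns AUC, the target-attainment simulation draws on Cmax and AUC0-12, and the hypothesis concerns concentrations. None of these uses F. This stands in full.

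**Conclusion.** The point holds in a conditional form. F is undefined, dialysate loss is the only fraction on offer, and using it as F makes IP clearance differ from IV clearance by f_a/F when true clearance is the same.

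The formula as printed overstates IP clearance, 1.5-fold at an assumed 2 L and 50% true loss. With amounts and drained-only counting, the overstatement is about 0.6% to 21% if later dwells absorb like the first and 2% to 35% if all residual drug is rinsed out. With whole-cavity counting the result is about unchanged or somewhat understated. All these sizes rest on assumed volumes, residual fractions and absorption, since the documents give none.

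A route comparison of clearance is uninformative either way: with dialysate loss as F it largely reflects the mismatch, plus noise and extrapolation error; with the correct F it is zero by construction. Exposed are IP clearance, the volume and non-dialysis clearance derived from it, and possibly the dosing model.

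**What to change.** In Section IV.F, Pharmacokinetic analysis:

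- State F = 1 for IV.
- Take systemic clearance, volume and non-dialysis clearance from the IV period, or from one joint IV and IP fit with common clearance and an estimated F.
- Add the within-patient ratio of AUC0-∞ after IP dosing to AUC0-∞ after IV dosing, analysed on the log scale, as the reported IP bioavailability.
- Report dialysate loss separately as an amount, concentration times volume, stating whether the volume is drained or total cavity volume. Name it as loss from dialysate and use it in no clearance formula.

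In Statistical comparisons of PK/PD findings, list the parameters to be tested between routes and leave clearance out. Correcting F alone would not rescue that test.

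The cost is analysis-plan wording plus, if the drained volume is used, a record of that volume. No extra samples or visits are needed. The downside is that clearance is no longer reported separately by route.

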### **II. Background and Significance:**

Every year in the United States approximately 110,000-115,000 patients are newly diagnosed with end-stage renal disease (ESRD) and begin treatment with renal replacement therapy. Nearly 10,000 of these patients are started on peritoneal dialysis (PD). The use of home dialysis has increased significantly (35% increase) in the last decade, with 95% of home dialysis patients undergoing PD. Infectious peritonitis is a leading major morbidity associated with PD, and it accounts for approximately 18% of infection-related mortality in PD patients. Severe or prolonged peritonitis can lead to peritoneal membrane failure, ultimately causing technical failure of PD and requiring transition to traditional hemodialysis methodologies. Rapid and effective treatment of peritonitis is required to reduce inflammation and preserve peritoneal membrane function. The current standard of care involves empiric antibiotics covering gram positive organisms as staphylococcus aureus, coagulase negative staphylococcus and enterococcus are common infecting pathogens. Vancomycin is commonly employed at most institutions as there is a risk of MRSA infections in this patient population. Addition of a second drug for gram negative bacteria coverage is recommended until culture and sensitivity results are available. Intravenous or intraperitoneal administration of antibiotics can be utilized; however, guidelines recommend the intraperitoneal administration of antibiotics with a dwell time of at least 6 hours because it provides instant, high, and sustained concentrations of the antibiotic in the peritoneal fluid. Although vancomycin covers the majority of gram positive organisms that cause peritonitis, its use can be cumbersome in PD patients. Plasma vancomycin drug concentration monitoring must occur to evaluate for vancomycin accumulation. Additionally, vancomycin must be re-administered every 3-5 days in order to maintain steady-state trough concentrations around 15 mcg/ml. Similarly to vancomycin, dalbavancin interferes with cell wall synthesis. This is done through binding of the D-alanyl-D-alanine terminus of the cell wall peptidoglycan. Dalbavancin has been shown to rapidly reach therapeutic systemic concentrations and to have an extended half-life of ~8.5 days. Dalbavancin has been shown safe and effective with a treatment doses of 1500 mg once or 1000 mg followed by a 500 mg dose on day 7. Dalbavancin pharmacokinetics were evaluated in patients who had hepatic or renal impairment. This study showed compared to healthy subjects dalbavancin exposure was not increased in mild renal impairment, exposure was ~50% higher in moderate renal impairment, 100% higher in severe renal impairment, and not significantly different in end stage renal disease

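### Plasma AUC0-∞ by linear trapezoid rests mostly on one line of about 160 h and a two-point tail, which weakens absolute exposure, clearance and volume

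*Combined protocol and SAP*

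**What the plan says.** Under Data Analysis Plan, Pharmacokinetic analysis, the area to infinity is assigned one method: "AUC_{0-\infty}$ – linear trapezoidal method". Systemic clearance divides the available dose by that area. Non-dialysis clearance and volume of distribution follow from clearance. There is no rule for the tail, for the number of terminal points, or for how much extrapolation is acceptable. The same section plans one-, two- and three-compartment fits, and a later NONMEM or ADAPT II step.

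The sampling times are in Study Design and Research Methods. On day 0 they are "time zero, 1 hour, 2 hours, 3 hours, 4 hours, 6 hours, at time of volume exchange". Section D gives the intensive visit a length of about 8 hours. Patients are then "asked to collect ~30 ml of peritoneal dialysate following scheduled nocturnal dwell approximately 24 hours following the administration", a home collection with no blood draw. After that, "Patients will report for a single PK measurement on study days 7 and 14".

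The Background says that dalbavancin was shown to "have an extended half-life of ~8.5 days". Under Statistical comparisons of PK/PD findings, a paired t-test is planned and the text says "we will be able to detect a mean difference in area under the curve between the two treatment modalities" (1527 mg·hr/L at 80% power). It does not say which AUC is meant.

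**The concern.** A trapezoidal AUC to infinity is reliable when samples follow the shape of the curve and the last one lies well down the terminal phase. Here neither holds for plasma. One straight line has to cross the whole period in which a multi-compartment drug would distribute, and a straight line drawn over a convex decline always encloses too much area. The tail depends on a slope that, on this schedule, has only two late points to rest on.

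Plasma pharmacokinetics is a primary endpoint. If AUC0-∞ is overstated, systemic clearance is understated, and the error passes into non-dialysis clearance and volume. If the paired test uses AUC0-∞, noise from time the trial never observes enters every patient's difference.

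**Working it through.** **Inputs from the plan.** Half-life 8.5 d = 204 h. Plasma at 0, 1, 2, 3, 4, 6 h and at exchange (up to about 8 h), then 168 h and 336 h.

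**The plan's own count.** (7 day-0 draws + day 7 + day 14) × 2 periods = 18 plasma samples, as stated, with none between discharge and day 7.

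**Follow-up.** 14/8.5 = 1.65 half-lives.

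**Case 1: one-exponential decline.** k = ln 2/204 = 0.003398 per h. The share of AUC0-∞ between t1 and t2 is exp(−k·t1) − exp(−k·t2).

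| Interval | Last day-0 draw at 6 h | at 8 h |
|---|---|---|
| Day-0 visit | 2.0% | 2.7% |
| To day 7 (one line) | 41.5% | 40.8% |
| Days 7-14 | 24.6% | 24.6% |
| Beyond day 14 | 31.9% | 31.9% |

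The line and the tail together make about 73%. For assumed half-lives of 6 to 12 d the sum stays at 71-76%, with the tail at 20-45%. The linear-trapezoid bias is only about 2%.

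*Precision, with an assumed 10% residual error per sample.* The CV of the two-point slope is √2 × 0.10/(168 × 0.003398) = 0.1414/0.571 ≈ 25%. In simulation (5th-95th percentiles):

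- Estimated half-life: about 6.0-14.3 d against a true 8.5 d.
- Tail: 0.62-1.92 of its true value.
- AUC0-∞: about 0.87-1.30 of truth (0.89-1.30 under the linear rule itself). The CV is about 15%, and because the distribution is skewed the percentiles are the better guide.
- AUC0-14d: CV about 6%.

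**Case 2: a distribution phase (assumed).** Distribution half-life 12-24 h, carrying a fraction f = 40-70% of the initial concentration; terminal half-life 8.5 d.

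One point of the grid by hand, as a bolus with initial concentration 1: half-life 24 h, f = 0.5, last day-0 draw at 6 h.

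- C(6) = 0.5 × 0.841 + 0.5 × 0.980 = 0.910
- C(168) = 0.5 × 0.0078 + 0.5 × 0.565 = 0.286
- Straight line, 6 to 168 h: 162 × (0.910 + 0.286)/2 = 96.9
- True area, 6 to 168 h: 0.5 × (24/ln 2) × (0.841 − 0.0078) + 0.5 × (204/ln 2) × (0.980 − 0.565) = 14.4 + 61.0 = 75.4
- True AUC0-∞: 0.5 × 24/ln 2 + 0.5 × 204/ln 2 = 164.5
- Excess from this one segment: 21.5/164.5 ≈ 13%

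Over the whole grid, with a 0.5 h infusion and the last day-0 draw at 6 h:

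| Quantity (intravenous) | Range |
|---|---|
| AUC0-14d, linear trapezoid | about 14-46% too high |
| AUC0-∞, linear trapezoid | about 10-33% too high |
| Systemic clearance | about 9-25% too low (1/1.10 = 0.91; 1/1.33 = 0.75) |
| True tail beyond day 14 | 25-31% of AUC0-∞ |
| AUC0-14d, log-down on falling segments | about 8-28% too high |

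**Effect on the route comparison.** With an assumed intraperitoneal absorption half-life of 2 h over the 6 h dwell, the linear rule moves the intraperitoneal/intravenous ratio by 0.5-2.9% for AUC0-∞ and by 0.8-3.7% for AUC0-14d.

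**The case against.** **The comparison is largely protected from the bias.** A reader might infer that a 10-33% error invalidates the comparison of routes. It does not: both routes share the schedule, and the ratio moves by less than 4% in the cases tried. A factor common to both routes still rescales a difference in mg·hr/L, and random tail error does not cancel within a patient, so part of the concern remains.

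**The AUC in the paired test is not named.** A reader might take the test and the 1527 mg·hr/L to refer to AUC0-∞. The documents do not say so. The only other window defined, AUC0-12, is no safe fallback for plasma, since the visit ends at about 8 h.

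**Compartment models are planned.** This is a fair point, and they can bridge the gap better than a straight line. But the plan assigns the trapezoid to AUC, and the models rest on the same two late plasma samples. Nor does the plan describe a joint fit across a patient's two periods.

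**There may be a 24 h plasma sample.** The stated counts of 18 plasma and 18 peritoneal samples would also fit six day-0 times plus 24 h, day 7 and day 14: (6 + 1 + 2) × 2 = 18. Appendix 2 allows 36 mL at 4 mL, or 9 draws, at the intensive visit against 7 listed times. Neither names an added plasma time, and both descriptions of the 24 h specimen concern dialysate collected by the patient.

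**Interpolation is not a fault in itself.** This is true, since every trapezoid interpolates. The fault is the length and position of this one, together with the missing tail rule. It is also true that the hypothesis concerns concentrations over two weeks, and that day 14 is measured directly. AUC0-14d fits that horizon but does not by itself test adequacy.

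**Conclusion.** The point holds as an improvement that should be made. The sampling facts are firm: one line to day 7 plus the tail carry about 73% of AUC0-∞ for a one-exponential decline at 8.5 d. That half-life is a background figure, not one measured in peritoneal dialysis patients, and the 32% tail should not be quoted without that condition.

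The size of the bias depends on a distribution phase that the documents do not quantify: about 2% without one, and about 10-33% in intravenous AUC0-∞ over the assumed grid. The consequence falls mainly on absolute AUC, clearance and volume. For the paired comparison the issue is precision, with a CV of about 15% for AUC0-∞ against about 6% for AUC0-14d under the assumed 10% error. The documents do not support a claim that the comparison of routes is materially biased.

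**What to change.** In **Pharmacokinetic analysis**:

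- Replace the linear trapezoid with linear-up/log-down for non-compartmental AUC.
- Take AUC0-∞ and clearance from the compartment model already planned.
- Report the percentage of AUC0-∞ extrapolated for each patient.

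In **Statistical comparisons of PK/PD findings**, name plasma AUC0-14d (0-336 h) as the AUC for the paired comparison of routes, with AUC0-∞ secondary.

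The two changes do different work. AUC0-14d removes the tail noise but not the linear bias, which is proportionally larger over 14 days. Log-down or the model deals with the bias, and log-down only in part. A joint fit across a patient's two periods is optional and would be new modelling.

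**Cost.** There is no added sample or visit, and a little more analysis work. The 1527 mg·hr/L must be restated for AUC0-14d together with its standard deviation, which the plan does not give. A two-sided paired t-test with n = 10 and 80% power needs a standardised difference of 0.996, so the figure implies an SD of paired differences of about 1527/0.996 = 1533 mg·hr/L. The model still depends on the same two late plasma samples, so uncertainty is reduced, not removed.

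### One expression, Cl/k_el, is given for the volume of every compartment and the same K_el defines half-life; in a two- or three-compartment model both cannot give what the plan labels them

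*Combined protocol and SAP*

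**What the plan says.** All of this stands in section IV.F of the combined protocol and SAP, under Pharmacokinetic analysis, unless stated otherwise.

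- The concentration-time data "will be evaluated using a multi-compartment model in Phoenix WinNonlin", and "One, two, and three compartment models will be explored".
- The list of parameters to be calculated includes K_el, described only as an elimination rate constant, and a half-life equal to 0.693/K_el.
- The same list includes "Volume of distribution for each compartment", given as Cl/k_el, with the remark that "nonsteady state equations will be utilized". No such equation is written out.
- No inter-compartmental clearance or rate constant is listed. The one distribution constant, K_pc0-6, describes loss from the peritoneal cavity over the first 6 hours.
- A later step reads "We will incorporate the dalbavancin PK parameters into a nonlinear mixed effects model (NONMEM) or ADAPT II", in part to "examine the effects of varying dosing strategies on plasma and peritoneal fluid concentrations".
- Section II gives dalbavancin an "extended half-life of ~8.5 days".

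Section IV.A makes plasma and peritoneal fluid pharmacokinetics the primary endpoints, so volume and half-life are primary outputs. Section IV.F says that parameters will be summarised by means and standard deviations.

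**The concern.** One clearance divided by one rate constant is one number. A two-compartment model has two volumes and a three-compartment model has three, so a single Cl/k_el cannot be the volume of each. Linking the same K_el to half-life makes the problem sharper. The constant that gives the terminal half-life is the terminal slope. The constant that turns clearance into the central volume is k10. They are equal only in a one-compartment model.

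An analyst who follows the text would therefore report a mislabelled volume, or a half-life that is not the terminal one, whenever more than one compartment is selected. The plan gives no way to tell which. Section IV.F also compares the two routes within patient, so K_el has to mean the same thing in both periods.

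**Working it through.** The documents state no volume, so there is no figure to reproduce. The check is algebra plus an illustration.

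**One compartment.** k10 equals the terminal slope, so Cl/K_el = V and 0.693/K_el is the half-life. Both formulas are correct.

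**Two compartments, notation.** V1 and V2 are the central and peripheral volumes, k12 and k21 the transfer constants, and alpha and beta the fast and terminal slopes. Then V1 = Cl/k10, V2 = V1 × k12/k21, Vss = V1 + V2 and Vz = Cl/beta.

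- If K_el = beta: Cl/K_el = Vz, and Vz/V1 = k10/beta. The half-life is the terminal one.
- If K_el = k10: Cl/K_el = V1 exactly and V2 is not obtained. The reported half-life is the terminal one divided by k10/beta.

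The same ratio, k10/beta, sets the size of either error.

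**Inputs.**

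- From section II: terminal half-life 8.5 days = 204 h, so beta = 0.693/204 = 0.00340 per h.
- Assumed, because the documents do not give them: distribution half-life 2 to 12 h, and distribution phase carrying a share A = 0.3 to 0.7 of the initial concentration, with B = 1 − A.

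**Formulas.** k21 = A × beta + B × alpha; k10 = alpha × beta/k21; k12 = alpha + beta − k21 − k10.

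**One corner in full** (distribution half-life 2 h, A = 0.7):

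- alpha = 0.693/2 = 0.3466 per h
- k21 = 0.7 × 0.00340 + 0.3 × 0.3466 = 0.1064 per h
- k10 = 0.3466 × 0.00340/0.1064 = 0.0111 per h
- k12 = 0.3466 + 0.0034 − 0.1064 − 0.0111 = 0.2325 per h
- Vz/V1 = 0.0111/0.00340 = 3.26
- V2/V1 = 0.2325/0.1064 = 2.19, so Vss/V1 = 3.19
- Vz/V2 = 3.26/2.19 = 1.49, and Vz/Vss = 3.26/3.19 = 1.02
- Half-life if K_el = k10: 8.5/3.26 = 2.6 days

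**All four corners.**

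| Distribution half-life | A | Vz/V1 | Vz/V2 | Vz/Vss | 0.693/k10 (days) |
|---|---|---|---|---|---|
| 2 h | 0.3 | 1.42 | 3.41 | 1.00 | 6.0 |
| 2 h | 0.7 | 3.26 | 1.49 | 1.02 | 2.6 |
| 12 h | 0.3 | 1.39 | 3.86 | 1.02 | 6.1 |
| 12 h | 0.7 | 2.93 | 1.83 | 1.13 | 2.9 |

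**Sensitivity to the assumptions.** A different grid, with the half-life still 204 h, takes V2/V1 from 0.5 to 4 and k21 from 0.01 to 0.1 per h. It gives Vz/V1 of 1.5 to 7.1 and Vz/V2 of 1.3 to 3.5. The direction is the same, but the size depends on what is assumed.

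**Three compartments, one assumed example** (V1, V2, V3 = 4, 3, 8 L). Cl divided by the terminal slope is 16.1 L, against a steady-state volume of 4 + 3 + 8 = 15 L. Cl/k10 is 4 L, the central volume. Neither gives the two peripheral volumes.

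**The case against.** The strongest reply is that the formula will hardly be used. The data are fitted with a compartmental model, the software returns the volumes, and nothing says that they will be discarded. The remark on non-steady-state equations also suggests that Cl/k_el is not the whole method. This makes harm less likely but does not remove the defect. The plan writes down a formula that disagrees with its own fit, does not say which value is reported, and names no equation that would settle it.

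The word compartment might instead mean plasma and peritoneal fluid, since the list covers both matrices. The plan does not say so. Even then, K_el is undefined, and a plasma Cl/K_el could be either the terminal-phase or the central volume.

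Four stronger readings are tempting but not supported.

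- **The central volume is wrong in every multi-compartment fit.** It is wrong only if K_el is the terminal slope. The half-life formula suggests that reading, but if K_el is k10 the central volume is exact.
- **Volume and half-life are both wrong.** The two errors belong to different definitions of K_el and are alternatives.
- **The error passes into the simulations.** The Monte Carlo target-attainment model draws Cmax and AUC0-12, and no volume enters. For NONMEM or ADAPT II, the plan mentions PK parameters in general and does not say that hand-calculated volumes are inputs. Such a model may estimate volumes itself.
- **The two-week conclusion is undermined.** Section IV.C measures plasma and peritoneal fluid concentrations directly on days 7 and 14.

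**Conclusion.** The point holds as a defect of definition in primary-endpoint outputs. When more than one compartment is selected, Cl/k_el and 0.693/K_el cannot both give what the plan labels them.

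- **K_el as terminal slope:** the reported volume is the terminal-phase volume, about 1.0 to 1.1 times steady-state volume but about 1.4 to 3.3 times the central volume.
- **K_el as k10:** the reported volume is the central volume only, peripheral volumes are missing, and the half-life is too short by a factor of 1.4 to 3.3.

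Only the 8.5-day half-life comes from the documents. The factors rest on the assumed distribution parameters and a two-compartment model; the algebra does not. Carry-over into the NONMEM or ADAPT II dosing work is a risk only if the hand-calculated volumes are used there. The plan should be corrected, but the defect does not threaten the design or the data to be collected.

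**What to change.** Amend section IV.F, Pharmacokinetic analysis, as follows.

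1. Define K_el as the terminal slope, and half-life as 0.693 divided by it, for both routes.
2. Report Cl/K_el once, for plasma, labelled as terminal-phase volume.
3. When a multi-compartment model is selected, report central, peripheral and steady-state volumes and inter-compartmental clearances from the fitted model in place of Cl/k_el.
4. State that any dosing simulation uses the fitted model parameters.
5. Either write out the non-steady-state equations or delete the remark.

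The cost is wording only. No sample, visit or assay is added, and the planned compartmental fit already supplies the parameters.
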